5.4 Dose Reduction Criteria

Subjects will reduce the dose through the IRS by one capsule per week, as necessary, and no more frequently than at biweekly intervals, in the event that any one of the following four criteria are met:

1. Two consecutive visits with plasma iPTH <35 pg/mL (for subjects with stage 3 CKD) or <70 pg/mL (for subjects with stage 4 CKD),
2. Two consecutive visits with serum calcium (corrected) >10.3 mg/dL,
3. Two consecutive visits with serum total 25-hydroxyvitamin D >100 ng/mL, or
4. Two consecutive visits with serum phosphorus >5.5 mg/dL (ages 12 to <18 years), or >6.0 mg/dL (ages 8 to <12 years) provided that the investigator has deemed the elevated serum phosphorus to be related to study drug administration and has taken appropriate and persistent actions to control serum phosphorus by initiating or adjusting any phosphate binder therapy.

Dose reductions will be accomplished by consistently omitting doses on a specific day of the week, as follows:

- First dose reduction: Dosing will be omitted on all M.
- Second dose reduction: Dosing will be omitted on all M and W
- Third dose reduction: Dosing will be omitted on all M, W and F

- Fourth dose reduction: Dosing will be omitted on all M, W, F and S

Any subject who requires a further dose reduction will terminate dosing with study drugs and commence the 6-week FU period.

Subjects on dose reduction will be allowed a safety visit if deemed appropriate by the investigator to have FU blood sampling within 48 hours of dose reduction.

A summary of the initial and reduced weekly dose levels, in mcg units, after each of the four possible dose reductions appears in the table below:

Daily (mcg)	Weekly					Dose (mcg)
	Weekly (mcg)	1 st Reduction	2 nd Reduction	3 rd Reduction	4 th Reduction	
60	420	360	300	240	180	
30	210	180	150	120	90	
0	0	0	0	0	0	

Subjects will suspend dosing if plasma iPTH is persistently <30 pg/mL (three consecutive visits) or serum calcium (corrected) is confirmed to be >11.0 mg/dL, and resume when iPTH is \geq 35 pg/mL (for subjects with stage 3 CKD) or \geq 70 pg/mL (for subjects with stage 4 CKD) and serum calcium is \leq 9.8 mg/dL at the next lower dose level.

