Subjects in both cohorts will reduce the dose by one capsule per week, as necessary, and no more frequently than at biweekly intervals, in the event that any one of the following four criteria are met: plasma iPTH is confirmed to be <35 pg/mL (for subjects with stage 3 CKD) or <70 pg/mL (for subjects with stage 4 CKD), serum calcium (corrected) is confirmed to be >10.3 mg/dL, serum total 25-hydroxyvitamin D is confirmed to be >100 ng/mL, or serum phosphorus is confirmed to be >5.5 mg/dL (ages 12 to <18 years) or >6.0 mg/dL (ages 8 to <12 years), provided that the investigator has deemed the elevated serum phosphorus to be related to study drug administration and has taken appropriate and persistent actions to control serum phosphorus by initiating or adjusting any phosphate binder therapy.

Dose reductions will be accomplished by consistently omitting doses on a specific day of the week, as follows:

- First dose reduction: Dosing will be omitted on all Mondays (M).
- Second dose reduction: Dosing will be omitted on all M and Wednesdays (W)
- Third dose reduction: Dosing will be omitted on all M, W and Fridays (F)
- Fourth dose reduction: Dosing will be omitted on all M, W, F and Sundays (S)

Any subject who requires a further dose reduction will terminate dosing with study drugs and immediately commence the 6-week FU period.

Subjects on dose reduction will be allowed an unscheduled safety visit if deemed appropriate by the investigator to have FU blood sampling within 48 hours of any dose reduction.

A summary of the initial and reduced weekly dose levels, in mcg units, after each of the four possible dose reductions appears in the table below:

Daily (mcg)	Weekly (mcg)	Weekly Dose (mcg)			
		1 st Reduction	2 nd Reduction	3 rd Reduction	4 th Reduction
60	420	360	300	240	180
30	210	180	150	120	90
0	0	0	0	0	0

Subjects will suspend dosing if plasma iPTH is persistently <30 pg/mL (three consecutive visits) or serum calcium (corrected) is confirmed to be >11.0 mg/dL, and resume when iPTH is ≥ 35 pg/mL and serum calcium is <9.8 mg/dL at the next lower dose level.

Primary Efficacy Endpoint:

The primary estimand is the reduction of mean plasma iPTH by at least 30% from pre-treatment baseline. The primary efficacy endpoint is the proportion of subjects in the intent-to-treat (ITT) population (age 8 to <18 years) attaining a mean decrease in plasma iPTH of at least 30% from pre-treatment baseline compared to placebo during the EAP.

Primary Safety Endpoints:

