5 STUDY TREATMENTS

5.1 Description of Treatments

5.1.1 *CTAP101 Capsules Description*

Dosage form: Soft capsule
Dose strength: 30 mcg capsule
Product description: Blue oval soft capsules containing white to off-white to slightly blue waxy material; 30 capsules per bottle
Active component: Calcifediol, calcidiol, 25-hydroxyvitamin D₃
Non-active components: Paraffin wax, mineral oil, mono- and diglycerides, dehydrated alcohol, lauroyl polyoxylglycerides, butylated hydroxytoluene, hypromellose, modified starch, carageenan, sodium phosphate dibasic, sorbitol and sorbitan solution, FD&C Blue #1, titanium dioxide, medium chain triglycerides (coconut oil)
Storage conditions: 15°C to 30°C (59°F to 86°F); protect from light and heat

5.1.2 *Placebo Capsules Description*

Dosage form: Soft capsule
Dose strength: 0 mcg capsule
Product description: Blue oval soft capsules containing white to off-white to slightly blue waxy material; 30 capsules per bottle
Active component: None
Non-active components: Paraffin wax, mineral oil, mono- and diglycerides, dehydrated alcohol, lauroyl polyoxylglycerides, butylated hydroxytoluene, hypromellose, modified starch, carageenan, sodium phosphate dibasic, sorbitol and sorbitan solution, FD&C Blue #1, titanium dioxide, medium chain triglycerides (coconut oil)
Storage conditions: 15°C to 30°C (59°F to 86°F); protect from light and heat

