5.3 Selection and Timing of Dose for Each Subject

Subjects in Cohort 1 will receive two capsules (CTAP101 Capsules and/or matching placebo capsules) every day at bedtime to achieve the targeted initial daily dose of 30 mcg of calcifediol (one CTAP101 Capsule plus one placebo capsule) or 0 mcg of calcifediol (two placebo capsules). Any food intake within 60 minutes of medication administration will also be recorded. At the end of 12 weeks of treatment, subjects assigned to active treatment will undergo upward dose titration to 60 mcg per day (two CTAP101 Capsules) provided that (a) plasma iPTH has not decreased by at least 30% from pretreatment baseline, (b) corrected serum calcium is <9.8 mg/dL, (c) serum phosphorus is \leq 5.5 mg/dL, and (d) serum total 25-hydroxyvitamin D is \leq 65 ng/mL. Subjects in Cohort 2 will receive a starting daily bedtime dose which will be determined on the basis of the interim analysis of data obtained in Cohort 1, and will undergo upward dose titration at the end of 12 weeks of treatment to a new daily dose that is two times higher than the starting dose, provided that (a) plasma iPTH has not decreased by at least 30% from pretreatment baseline, (b) corrected serum calcium is <9.8 mg/dL, (c) serum phosphorus is \leq 6.0 mg/dL and (d) serum total 25-hydroxyvitamin D is \leq 65 ng/mL.

In order to maintain blinding, subjects will receive periodic supplies of study drug in bottles of identical appearance, some labeled “Bottle 1” and some labeled “Bottle 2,” along with the same dosing instructions regardless of randomization group directing the subject to take one capsule from one bottle labeled “Bottle 1” and one bottle labeled “Bottle 2” every day at bedtime.

An unblinded medical monitor who will be part of the independent, unblinded DSMB will oversee study drug assignments and dose adjustments (see below) by IRS.

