9.10 Efficacy Analysis

9.10.1 *Primary Endpoint Analysis*

Primary efficacy will be assessed in the ITT population by comparing the proportions of subjects in each treatment group (CTAP101 Capsules versus placebo) attaining a mean decrease from baseline in plasma iPTH of $\geq 30\%$ in the EAP using the Cochran-Mantel-Haenszel test statistic (alpha=0.05) for overall efficacy of the multicenter results. Subjects who do not have at least two plasma iPTH determinations in the EAP will be deemed non-responders.

9.10.2 *Secondary Endpoint Analyses*

Secondary efficacy will be assessed in the PP population by comparing the proportions of subjects in each active treatment group attaining mean decreases in plasma iPTH of $\geq 30\%$ from baseline in the EAP to the corresponding proportion of subjects in the placebo group, and in the ITT and PP populations by comparing the proportions of subjects in each active treatment group attaining mean serum total 25-hydroxyvitamin D of ≥ 30 ng/mL in the EAP to the corresponding proportions of subjects in the placebo group, in aggregate and by mean weekly study dose in the EAP. Mean weekly dose in the EAP will be calculated for two groups of subjects: those receiving ≤ 30 mcg per day; and those receiving > 30 mcg/day. Secondary efficacy will also be assessed by the time courses of mean absolute changes from pre-treatment baseline in serum total 25-hydroxyvitamin D and plasma iPTH (i.e., continuous iPTH change); and pharmacodynamic (PD) effects on mean serum calcium (corrected), serum phosphorus, serum [REDACTED], and the urine calcium:creatinine ratio.

- [REDACTED]

The number (n, %) of subjects attaining two consecutive reductions in plasma iPTH values $\geq 30\%$ from baseline, as well as, the number (n, %) subjects with two consecutive plasma iPTH values ≤ 70 pg/mL will be compared between treatment groups.

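### The dose-reduction rule is worded as one capsule per week, but the omitted-day list and the table remove a whole day's dosing; at 60 mcg/day the two differ twofold in step size

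*Combined protocol and SAP*

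**What the plan says.** Section 5.4 of the combined protocol and SAP begins "Subjects will reduce the dose through the IRS by one capsule per week". The Dosing Plan in the synopsis has the same rule: "Subjects in both cohorts will reduce the dose by one capsule per week".

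Both places then describe how the reduction is made. Doses are left out on fixed weekdays, one further weekday per step: "First dose reduction: Dosing will be omitted on all M", then Monday and Wednesday, then Friday as well, then a fourth day. Both print the same table of weekly doses for starting levels of 60, 30 and 0 mcg/day. A subject who would need a fifth reduction stops study drug and enters follow-up.

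The capsule count comes from Section 5.3: "Subjects in Cohort 1 will receive two capsules (CTAP101 Capsules and/or matching placebo capsules) every day at bedtime". Section 5.1 gives the active product as "Dose strength: 30 mcg capsule". The lower active dose is made up as "30 mcg of calcifediol (one CTAP101 Capsule plus one placebo capsule"; the 60 mcg dose is two active capsules.

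Two later rules use the dose or the capsule count. Section 9.10.2 says "Mean weekly dose in the EAP will be calculated for two groups of subjects", split at 30 mcg/day. The synopsis has three groups, with placebo separate, but the same cut at 30. Section 5.10 defines compliance as capsules taken against capsules due, and a result under 80% is reported as a deviation.

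**The concern.** A Cohort 1 subject takes two capsules on each dosing day, so leaving out a day removes two capsules. The opening sentence says one. The same rule is therefore stated in two ways that cannot both hold for a subject on 60 mcg/day.

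This is the operative response to high corrected calcium, high 25-hydroxyvitamin D, drug-related high phosphorus and over-suppressed iPTH. It also fixes how much exposure has been withdrawn by the time a fifth reduction would end treatment. Whoever programs the IRS, writes the instructions to families or sets the expected capsule count needs a single version to work from.

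**Working it through.** **Inputs.** Active capsule 30 mcg (Section 5.1). Two capsules per dosing day in Cohort 1, one active plus one placebo at 30 mcg/day and two active at 60 mcg/day (Section 5.3). Up to four reductions, and the weekly dose table (Section 5.4 and synopsis). Let k be the number of reductions made.

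**Step 1: reproduce the table.** With k weekdays omitted, weekly dose = daily dose × (7 − k).
- 60 mcg/day: 60 × 7, 6, 5, 4, 3 = 420, 360, 300, 240, 180.
- 30 mcg/day: 30 × 7, 6, 5, 4, 3 = 210, 180, 150, 120, 90.
- 0 mcg/day: 0 throughout.

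Every cell matches the printed table.

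**Step 2: apply the sentence literally at 60 mcg/day.** Weekly dose = 420 − 30k; divide by 7 for the daily average.

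| k | Table, mcg/week | Sentence, mcg/week | Table, mcg/day | Sentence, mcg/day |
|---|---|---|---|---|
| 0 | 420 | 420 | 60.0 | 60.0 |
| 1 | 360 | 390 | 51.4 | 55.7 |
| 2 | 300 | 360 | 42.9 | 51.4 |
| 3 | 240 | 330 | 34.3 | 47.1 |
| 4 | 180 | 300 | 25.7 | 42.9 |

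Step size is 60 mcg (60/420 = 14.3%) by the table and 30 mcg (30/420 = 7.1%) by the sentence, a ratio of 2. After four steps the weekly dose is down 240/420 = 57.1% or 120/420 = 28.6%.

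**Step 3: the same at 30 mcg/day.** If the capsule is an active one, 210 − 30k = 180, 150, 120, 90, identical to the table. The mcg conflict does not arise here.

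**Step 4: physical capsules per week, any arm.** Omitted days: 14 − 2k = 14, 12, 10, 8, 6. Sentence: 14 − k = 14, 13, 12, 11, 10. The counts disagree at every dose level, placebo included.

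**Step 5: the analysis cut.** From the table in Step 2, both readings stay above 30 mcg/day after one, two or three reductions. They separate only after the fourth: 25.7 against 42.9.

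**Step 6: compliance.** The plan does not say how the number of capsules due is set after a reduction. If, as an assumption, it were set from the sentence, a subject who follows the day list exactly would score 12/13 = 92%, 10/12 = 83%, 8/11 = 73% and 6/10 = 60% in weeks at levels one to four, so below 80% at the third and fourth. Capsules are counted at Visits 13 and 22 (Section 6.5), so weeks at other levels would dilute these figures. If the number due follows the day list, the problem disappears.

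**The case against.** The best reply is that the section resolves itself. Directly after the criteria it states the method, names the days and tabulates the dose at each step, and the two specific statements agree in every cell. The 390, 360, 330, 300 series is printed nowhere, and following it would mean ignoring both the list and the table. Reductions also go through the IRS, with an unblinded medical monitor overseeing dose adjustments. All of that stands. It makes the sentence the outlier, but it does not show which version the IRS is programmed to.

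Several stronger readings are tempting, and the documents do not support them:

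- **That the rule is ambiguous at 30 mcg/day, so a site could drop the placebo capsule and leave the dose unchanged.** Nothing tells a site or family to omit one capsule from one bottle. Section 5.3 pairs the two bottles under the same instructions for all groups, and Section 5.4 omits dosing on the named day. The zero-change outcome requires acting against the stated method.
- **That the secondary dose groups are broadly affected.** Only the fourth reduction from 60 mcg/day crosses the cut, and the groups are defined by the dose subjects receive.
- **That the table contains an arithmetic error.** It does not; this is inconsistent wording.
- **That every subject in both cohorts takes two capsules.** The explicit statement covers Cohort 1. The bottle instruction is general, but the Cohort 2 starting dose is not yet set.

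**Conclusion.** The contradiction is real and should be corrected. It is confined to the opening sentence of the rule, in Section 5.4 and the synopsis, set against the list and table in the same places. For Cohort 1 at 60 mcg/day the step sizes differ by a factor of two, and after four steps the weekly doses are 180 and 300 mcg. At 30 mcg/day only the capsule count disagrees, provided that an active capsule is meant.

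The statistical reach is small. The primary comparison is between randomized groups and does not use the dose groups, and no sample size, power or alpha figure depends on this point. The compliance effect is conditional on how the expected count is built. The point deserves attention because it sits in a safety rule, not because it threatens the efficacy conclusion. Nothing here says which reduction is clinically right.

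**What to change.** Reconcile the opening sentence, the omitted-day list and the table in Section 5.4 and in the synopsis, so that a single rule is stated in both days and capsules, with the resulting weekly dose. The sponsor's clinicians decide which rule stands. Then confirm that the IRS is programmed to that rule and that the number of capsules due in the Section 5.10 compliance calculation follows it after each reduction. When the Cohort 2 starting dose is set, check that the capsule count and the table still apply to it.

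Cost: wording in two places, an IRS check and one line on the compliance count. No analysis or sample size changes.

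### Dosing is suspended only on a confirmed corrected calcium above 11.0 mg/dL, but the confirming test is not timed and drug is not held meanwhile, so a site may (but need not) dose on to the next visit

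*Combined protocol and SAP*

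**What the plan says.** Section 5.4 and the Dosing Plan in the Synopsis suspend dosing for calcium when "serum calcium (corrected) is confirmed to be >11.0 mg/dL". The same sentence has a separate iPTH trigger, a value below 30 pg/mL, for which it asks for three visits in a row. For calcium it gives no visit count, no time for the confirming test and no interim hold. Section 3.2 also speaks of acting on confirmed elevations, so waiting for confirmation is intended. What is missing is when to confirm.

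Other text that bears on the point:

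- Section 6.4.2 confines redraws of missing samples, and of values outside the entry ranges, to screening. It also says that unscheduled or repeat visits may call for extra draws.
- Section 5.4 allows a safety visit within 48 hours of a dose reduction, if the investigator wants one.
- Section 5.3 has an unblinded medical monitor overseeing dose adjustments.
- Section 6.8 lets the investigator withdraw a subject for a clinically significant laboratory change.
- Table 2 marks iPTH, total 25-hydroxyvitamin D and 25-hydroxyvitamin D₃ as blinded. Calcium is not, so sites see it.

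**The concern.** If *confirmed* means two consecutive visits, a first calcium above 11.0 mg/dL after a normal visit calls for no more dose action than a first value of 10.4 mg/dL. Two sites following the same text could stop drug within days or only about two weeks later.

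Section 5.5 explains why that matters. Worsening hypercalcemia can become an emergency, the product has no specific antidote, and the half-life in adults with stage 3 or 4 CKD is about 30 days, so extra exposure clears slowly. Section 1.13 adds that the product has not been studied in children before.

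**Working it through.** **1. What *confirmed* means elsewhere.** The four dose-reduction criteria appear twice, in different words:

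| Criterion | Synopsis, Dosing Plan | Section 5.4 |
|---|---|---|
| iPTH | "plasma iPTH is confirmed to be <35 pg/mL" | "Two consecutive visits with plasma iPTH <35 pg/mL" |
| Calcium | "serum calcium (corrected) is confirmed to be >10.3 mg/dL" | "Two consecutive visits with serum calcium (corrected) >10.3 mg/dL" |
| Total 25D | "serum total 25-hydroxyvitamin D is confirmed to be >100 ng/mL" | "Two consecutive visits with serum total 25-hydroxyvitamin D >100 ng/mL" |
| Phosphorus | "serum phosphorus is confirmed to be >5.5 mg/dL" | two visits in a row above the same limit |

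The safety analysis of calcium above 10.3 mg/dL shows the same pairing: *confirmed* in the Synopsis (Statistical Analyses), two visits in a row in Section 9.11.2. Carrying that meaning over to the 11.0 mg/dL rule is an inference, not something the text states.

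**2. The redraw limit.** Entry calcium must be below 9.8 mg/dL (Section 4.2, criterion 4b). A value above 11.0 lies outside that range, so read literally the redraw sentence in Section 6.4.2 discourages a repeat after screening.

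**3. Length of the wait.** Readable treatment days in Appendix 1 are 1, 8, 15, 22, 29, 43, 57, 71, 83, 84, 85 and 92, then 155, 169 and 183.

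- Gaps: 7, 7, 7, 7, 14, 14, 14, 12, 1, 1 and 7 days, then 14 and 14 days.
- Five gaps of 14 days: 29–43, 43–57, 57–71, 155–169 and 169–183.
- 5 × 14 = 70 days, and 70/182 = 38%.
- This is a lower bound, because the days for Visits 15–19 are not readable in the extracted schedule. Visits 14 and 16 are only for titrated subjects (Section 7.2.4). Everyone else has Visits 15, 17, 18 and 19 between Days 85 and 155: five gaps in 70 days, averaging 14.
- With the ±3-day windows, the first four 14-day gaps can run from 8 to 20 days. The last can run from 11 to 17, because Day 183 is fixed.

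**4. Dose taken during a wait (Cohort 1).** 14 × 30 = 420 mcg. Windows give 8 × 30 = 240 to 20 × 30 = 600 mcg. At 60 mcg/day, 14 × 60 = 840 mcg; among the printed gaps this is possible only in the last two, after titration. Cohort 2's dose is not fixed in the documents.

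**5. What a timed repeat and a hold each save.** Samples go to a central laboratory (Section 6.4.2), and turnaround is not given. Let it be *t* days per result, with the full 72 hours running from the first result and a 14-day gap. Days count from the first high sample.

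- Waiting for the next visit: dosing stops on day 14 + t.
- Repeat within 72 hours, no hold: dosing stops on day t + 3 + t = 2t + 3.
- Hold on the first result: dosing stops on day t.
- The repeat saves (14 + t) − (2t + 3) = 11 − t days. The hold saves a further (2t + 3) − t = 3 + t days. Together they save 14.
- A false alarm costs 3 + t doses.

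| t (assumed) | Repeat saves | Hold adds | Doses lost in a false alarm |
|---|---|---|---|
| 0 | 11 days | 3 days | 3 (3/182 = 1.6%) |
| 2 | 9 days | 5 days | 5 (5/182 = 2.7%) |
| 4 | 7 days | 7 days | 7 (7/182 = 3.8%) |

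**6. Exposure.** Under linear kinetics, omitting 14 daily doses lowers 25-hydroxyvitamin D₃ by 1 − 2^(−14/h) of its steady-state baseline-adjusted level, where h is the half-life in days. Using the adult range of 25 to 50 days (Section 1.12), this is 32.2% at h = 25, 27.6% at h = 30 and 17.6% at h = 50. If decay starts 43 hours after the last dose (the upper adult t_max), the figures are 28.7%, 24.6% and 15.6%. The range is about 16–32%.

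**The case against.** The strongest reply is that Section 5.4 counts visits wherever it wants visits counted: in all four reduction criteria and, in the suspension sentence itself, for iPTH. Only calcium above 11.0 mg/dL gets the bare word *confirmed*, and that contrast favours a prompt repeat. Even if two visits are needed, an unscheduled visit could be the second. Sites see calcium, may draw unscheduled samples and may withdraw the subject. A medical monitor oversees dose adjustments, and the DSMB charter and laboratory manual, which are not in the documents, may hold an alert rule. Events should be few: entry calcium is below 9.8 mg/dL, and the adult mean rise was 0.2 versus 0.1 mg/dL on placebo (Section 1.13).

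Much of this stands. A reader might infer that the protocol obliges sites to dose on for two weeks; it does not. A reader might also infer harm from raised calcium, but the documents give neither a calcium response nor a rate of values above 11.0.

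The gap remains all the same. The safeguards in the documents are discretionary or do not time the repeat; the 48-hour visit is optional and follows a dose reduction that a first high value does not trigger. A safety stopping rule with two fair readings should be settled in its own text.

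**Conclusion.** The point holds as a gap in a safety rule that should be closed. The written rule permits, but does not require, dosing on to the next visit after a first corrected calcium above 11.0 mg/dL. The next visit is 14 days away in five printed intervals, at least 70 of 182 treatment days, and a 14-day wait means 420 mcg at 30 mcg/day in Cohort 1. The 38% share is a floor, not the full figure.

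The size is drug exposure only, and the 16–32% figure rests on adult half-lives and linear kinetics. A reader might also infer that the timed repeat brings most of the benefit and the hold little. That is so only if results come back at once. At an assumed turnaround of 4 days the two are equal, and turnaround is not given.

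**What to change.** Add to Section 5.4 and the Synopsis, for both arms:

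- On receipt of a first corrected calcium above 11.0 mg/dL, hold study drug and repeat calcium and albumin at an unscheduled visit within 72 hours (interval for clinicians to set).
- Repeat above 11.0: the value is confirmed, and the suspension and resume rule applies.
- Repeat above 10.3 and up to 11.0: reduce the dose as under criterion 2, subject to the biweekly limit.
- Repeat 10.3 or lower: resume the same dose.

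State in Section 6.4.2 that its redraw limit does not apply to safety repeats.

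Leave the hypercalcemia endpoint in Section 9.11.2 as it is. It refers to consecutive visits, not scheduled ones. Barring the unscheduled repeat from counting would narrow it: a child at 11.4, confirmed at 11.3 on day 3 and suspended, then at 10.3 or lower at the next scheduled visit, would drop out of the active-versus-placebo comparison.

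The cost is one short paragraph in two places, one sentence in Section 6.4.2, one small sample per event, and about 3 + t missed doses in a false alarm. Blinding is unaffected, because sites already see calcium and the rule is the same in both arms.
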